- Evaluable for response analysis set is a subset of patients in the FAS who had measurable disease at baseline.
- The safety analysis set (SAS) will consist of all patients who received any amount of study treatment. Safety data will be summarized using the SAS according to the treatment received.
- The DLT evaluable analysis set is a subset of the SAS for the dose-finding phase of the study. It includes all patients enrolled in the dose-finding phase of the study who receive the protocol-assigned treatment with durvalumab + tremelimumab and complete the safety follow-up through the DLT evaluation period (Cycle 1 + Cycle 2) or experience a DLT during the DLT evaluation period.
- The PK analysis set will consist of all patients who receive at least 1 dose of IP per the protocol for whom any postdose data are available and who do not violate or deviate from the protocol in ways that would significantly affect the PK analyses. The population will be defined by the Study Physician, Pharmacokineticist, and Statistician prior to any analyses being performed.

The analysis of the primary endpoint, ORR, and the analyses of the secondary endpoints, progression-free survival (PFS), duration of response (DoR), and disease control rate (DCR), will be based on the site Investigator assessments using Response Evaluation Criteria in Solid Tumors (RECIST) 1.1 for solid tumors. Immune-related Response Evaluation Criteria will also

be assessed for ORR and PFS. In addition, OS, another secondary endpoint, will also be evaluated.

The 2 phases of the study will be summarized and analyzed separately. For the dose-finding phase, summaries will be presented by DL. For the dose-expansion phase, summaries and analyses will be presented by cohort.

Methods for statistical analysis:

The following table presents the analyses planned for the efficacy endpoints. All tumor-related endpoints will be analyzed using Investigator RECIST 1.1 assessments.

Pre-planned statistical analyses to be conducted

Endpoints analyzed	Notes
Objective response rate	Exact 90% 2-sided CI (Mid-P)
Duration of response	Median estimated from KM curve
Disease control rate	Exact 90% 2-sided CI (Mid-P)
Best objective response	n (%) of patients in each response category
Progression-free survival	Median estimated from KM curve
Overall survival	Median estimated from KM curve
Proportion alive and progression-free at 12 months	90% 2-sided CI estimated from KM curve
Proportion alive and progression-free at 18 months	90% 2-sided CI estimated from KM curve
Proportion alive at 12 months	90% 2-sided CI estimated from KM curve
Proportion alive at 24 months	90% 2-sided CI estimated from KM curve

CI Confidence interval; KM Kaplan-Meier.

No multiplicity adjustment will be applied.

Safety and tolerability data will be presented by DL in dose-finding phase and by cohort in dose-expansion phase, using the SAS. Data from all cycles of treatment will be combined in the presentation of safety data.

Safety and tolerability will be assessed in terms of AEs (including SAEs), deaths, laboratory data, vital signs, ECGs, physical examinations and exposure to durvalumab + tremelimumab combination therapy, and durvalumab monotherapy. Time on study, durvalumab + tremelimumab combination therapy, and durvalumab monotherapy dose delays will also be summarized.

Pharmacokinetic data will be summarized and analyzed based on the PK analysis set.

Pharmacokinetic concentration data will be listed for each patient and each dosing day and a summary will be provided for all evaluable patients.

Immunogenicity results will be listed by patient, and a summary will be provided by the number and percentage of patients who develop detectable anti-durvalumab and anti-tremelimumab antibodies. The immunogenicity titer and neutralizing ADA data will be listed for samples confirmed positive for the presence of anti-durvalumab or anti-tremelimumab antibodies.

Vaccine individual antibody titer data and CCI data will be listed for each patient and a summary will be provided.

[figure not shown]
The relationship of CCI to clinical outcomes (including but not restricted to) of ORR, DCR, PFS and OS will be presented.

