For the SARCOMA cohort, the initial stage will allow 11 evaluable patients, to be dosed in this disease-specific cohort. If 2 or more responses in either of these cohorts are observed, additional patients will be accrued, as part of the second stage, into the corresponding expansion cohort; 15 patients will be accrued into the SARCOMA expansion cohort for a total of 26 evaluable patients. If there has been ≤ 1 objective response in the SARCOMA cohort (11 patients), at the time that evaluable patients dosed in the initial stage have been followed/assessed for at least 3 cycles, the cohort will be discontinued for lack of benefit.

For the STO cohort, 10 evaluable patients will be enrolled into this mixed-disease cohort; Simon rules are not applicable for this cohort.

Study period:

Date of first patient enrolled: Q1 2019.

Estimated date of last patient completed: Q1 2023.

Number of patients:

Dose-finding phase: The final sample size in the dose-finding phase will depend on the number of DLTs and on the number of DLs to be explored. In addition, any patients not evaluable will be replaced in order to have the required number of patients evaluable at each DL. A minimum of 12 patients is anticipated to be dosed, to enable exploration of one DL in both patients weighing 35 kg and greater, and patients weighing under 35 kg. If all 3 DLs are used at both weight-based arms, then 36 evaluable patients would be necessary to complete the dose-finding phase. If approximately 20% of patients need to be replaced due to non-evaluability, then a maximum of 45 patients will be enrolled on the dose-finding cohorts.

Dose-expansion phase:

- Following a Simon 2-stage optimal design, a total of 26 evaluable patients (11 evaluable patients in the initial stage and an additional 15 patients in the second stage), are expected to be enrolled in the SARCOMA cohort.
- The STO cohort is planned to recruit 10 evaluable patients.

With the above considerations, the sample size for evaluable patients in the dose-expansion phase is expected to range from 38 to 66. Assuming that about 20% of patients may not be evaluable for objective response rate (ORR), the total number of patients dosed in the dose-expansion phase may range from approximately 46 to 80.

Screen failures are patients who do not fulfill the eligibility criteria for the study, and therefore must not be dosed. Patients may be rescreened a single time.

Treatments and treatment duration:

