4.1.4 Dose-expansion phase

During dose-expansion, patients will be monitored for safety according to the same criteria employed during the dose-finding phase (although events will not be considered DLTs during dose-expansion). Additionally, 4 cycles of safety information are required prior to opening the initial dose-expansion cohorts. See Section 4.1.2 for stopping criteria.

The dose-expansion phase will be conducted using a Simon 2-stage optimal design with an additional provision to include 1 mixed disease cohort (other malignant solid tumors).

Once the RP2D has been established, patients will be recruited to each of the following cohorts:

1. SARCOMA (bone sarcomas: osteosarcoma and Ewing sarcoma; soft-tissue sarcomas [$\geq 40\%$ of enrollment]: rhabdomyosarcoma, non-rhabdomyosarcoma, and other sarcomas)
2. STO (other solid tumors).

For the SARCOMA cohort, the initial stage will allow 11 evaluable patients, to be dosed in this disease-specific cohorts. If 2 or more responses in either of these cohorts are observed, additional patients will be accrued, as part of the second stage, into the corresponding expansion cohort; 15 patients will be accrued into the SARCOMA expansion cohort for a total of 26 evaluable patients. If there has been ≤ 1 objective response in either cohort, at the time that evaluable patients (11 patients) dosed in the initial stage who have been followed for at least 3 cycles have been assessed, the cohort will be discontinued for lack of benefit.

For the STO cohort, 10 evaluable patients will be enrolled into this mixed-disease cohort; Simon rules are not applicable for this cohort.

4.1.5 Study Conduct Mitigation During Study Disruptions Due to Cases of Civil Crisis, Natural Disaster, or Public Health Crisis

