With the above considerations, the sample size for evaluable patients in the dose-expansion phase is expected to range from 21 to 36. Assuming that about 20% of patients may not be evaluable for ORR, the total number of patients dosed in the dose-expansion phase may range from approximately 25 to 43.

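### The Synopsis dose-expansion total (38 to 66 evaluable, about 46 to 80 dosed) does not follow from its own two cohorts, which sum to 21 to 36

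*Protocol*

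**What the plan says.** Under Number of patients, the Protocol Synopsis (Section 1.2) builds the dose-expansion sample size from two cohorts. For SARCOMA it plans "a total of 26 evaluable patients (11 evaluable patients in the initial stage and an additional 15 patients in the second stage". For the mixed cohort, "The STO cohort is planned to recruit 10 evaluable patients", and the Simon rules do not apply to it. The Synopsis then draws its total from these considerations: "the sample size for evaluable patients in the dose-expansion phase is expected to range from 38 to 66". After allowing for about 20% of patients not being evaluable for objective response, "the total number of patients dosed in the dose-expansion phase may range from approximately 46 to 80".

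Protocol Section 9.2 starts from the same two cohorts and the same 20% allowance but reaches a different total: "the sample size for evaluable patients in the dose-expansion phase is expected to range from 21 to 36", with about 25 to 43 dosed. SAP Section 1.3 gives the same figures as Section 9.2.

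The cohort targets are not in dispute. Protocol Section 4.1.4 repeats that "15 patients will be accrued into the SARCOMA expansion cohort for a total of 26 evaluable patients" and that STO takes 10, and SAP Sections 1.2 and 1.3 agree.

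**The concern.** A total that is said to follow from listed components should equal their sum, and here it does not. The current protocol therefore carries two incompatible planned sizes for the same phase, one in the Synopsis and one in Section 9.2.

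The Synopsis is where many readers take the planned enrollment from. In this trial that figure is the number of children expected to receive an investigational combination. A reader relying on it would expect almost twice the planned expansion exposure. Actual accrual could also be reported against either of two targets.

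**Working it through.** **Inputs**

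- SARCOMA, stage 1: 11 evaluable (Synopsis; Sections 4.1.4 and 9.2; SAP 1.2 and 1.3).
- SARCOMA, both stages: 11 + 15 = 26 evaluable (same places).
- STO: 10 evaluable, fixed (same places).
- Not evaluable for response: about 20% (Synopsis; Section 9.2; SAP 1.3).
- Number of expansion cohorts: two (Synopsis; Table 7 in Section 4.1; Section 4.1.4; SAP Table 2).

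**Evaluable patients**

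- Minimum = SARCOMA stage 1 + STO = 11 + 10 = 21.
- Maximum = SARCOMA total + STO = 26 + 10 = 36.

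This reproduces Section 9.2 and SAP 1.3 exactly. It does not reproduce the Synopsis, whose lower limit of 38 exceeds the maximum of 36.

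**Dosed patients**

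There are two common ways to allow for 20% non-evaluable patients:

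| Evaluable | n × 1.2 | n / 0.8 |
|---|---|---|
| 21 | 25.2 | 26.25 |
| 36 | 43.2 | 45 |
| 38 | 45.6 | 47.5 |
| 66 | 79.2 | 82.5 |

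The 25 to 43 in Section 9.2 and SAP 1.3 is 21 to 36 multiplied by 1.2. The Synopsis range of 46 to 80 is 38 to 66 multiplied by 1.2. Neither method takes 21 to 36 to 46 to 80, so the dosed range simply inherits the error in the evaluable range.

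**Size of the discrepancy**

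| | Synopsis | Section 9.2 and SAP 1.3 | Excess | Ratio |
|---|---|---|---|---|
| Evaluable, minimum | 38 | 21 | 17 | 1.81 |
| Evaluable, maximum | 66 | 36 | 30 | 1.83 |
| Dosed, minimum | 46 | 25 | 21 | 1.84 |
| Dosed, maximum | 80 | 43 | 37 | 1.86 |

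**Whole study**

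For dose finding the Synopsis says "A minimum of 12 patients is anticipated to be dosed" and, at the upper end, "then a maximum of 45 patients will be enrolled on the dose-finding cohorts". Adding these to the dosed ranges:

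- Minimum: 12 + 46 = 58 against 12 + 25 = 37, a ratio of 1.57.
- Maximum: 45 + 80 = 125 against 45 + 43 = 88, a ratio of 1.42.

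**Are the cohort sizes themselves sound?**

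Section 9.2 sets a null response rate of 10%, an alternative of 30%, a one-sided type I error of 0.1 and power of at least 85%. The cohort continues with 2 or more responses in 11 patients, and the null is rejected with 5 or more in 26. For a true rate p, the probability of rejection is

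Σ (x = 2 to 11) P(Bin(11, p) = x) × P(Bin(15, p) ≥ 5 − x).

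This gives 0.0865 at p = 0.10 and 0.8516 at p = 0.30. A search over two-stage designs under these constraints returns the same design as the Simon optimal one. The components stand, and only the Synopsis total is wrong.

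**The case against.** The strongest reply is that this is carry-over text with no operational effect. The version history records 38 to 66 and 46 to 80 as the version 5.0 figures. A later entry removes the non-Hodgkin's lymphoma cohort and limits STO to 10. Every section that governs conduct or analysis carries the right targets, as does the Synopsis itself one sentence earlier, and no stopping rule, analysis set or estimate uses 38 to 66. All of that is correct and sets the weight of the point. It does not defend the sentence, which is current protocol text and contradicts other current text.

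A second objection is to the whole-study ratios. The minimum adds dose-finding patients counted without replacements to an expansion figure that includes an allowance. The maximum adds 45 enrolled patients to a dosed range, although Section 5 defines enrolled as having signed consent. The sums are right, but they are only a rough guide, and the conclusion does not need them.

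A third is that 25 to 43 may itself be slightly low. If 20% of dosed patients are not evaluable, 25 dosed gives 20 evaluable and 43 gives 34.4, just under 21 and 36. Dividing by 0.8, as the dose-finding maximum does (36 / 0.8 = 45), would give about 27 to 45. The gap is about 2 patients in a range labelled approximate. It does not rescue 46 to 80 and is no reason to delay the correction.

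**Conclusion.** The Synopsis total is wrong as written. From the cohorts it lists, the dose-expansion phase needs 21 to 36 evaluable patients, not 38 to 66. On the multiplication the sponsor uses, that means about 25 to 43 dosed, not 46 to 80. The overstatement is about 1.8-fold for the expansion phase and roughly 1.4- to 1.6-fold for the whole study.

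The evaluable figures rest only on there being two expansion cohorts of the stated sizes, on which the current design sections of both documents agree. The dosed figures also rest on the 20% allowance. This should be corrected, but it is a consistency error in a headline number and has no consequence for inference.

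**What to change.** In the Synopsis, Number of patients, change the evaluable range from 38 to 66 to 21 to 36, and the dosed range from 46 to 80 to 25 to 43, matching Section 9.2 and SAP Section 1.3. Leave those two sections and the cohort targets of 11, 26 and 10 as they are.

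The cost is two ranges in one paragraph, with no change to design, error rates, power or analysis.

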1.3 Schema

The general study design is summarized in [Figure 1](#).

Figure 1 Study design

This figure shows the maximum doses at dose-finding for durvalumab at DLs 2 and 3 (40 mg/kg) and tremelimumab at DL 3 (2 mg/kg). Lower doses may be tested, depending on the obtained PK modeling data

DL Dose level, NB Neuroblastoma; SARC-1 Osteosarcoma and Ewing sarcoma; SARC-2 Rhabdomyosarcoma, non-rhabdomyosarcoma, and other sarcomas; SARCOMA Osteosarcoma and Ewing sarcoma, and Rhabdomyosarcoma, non-rhabdomyosarcoma, and other sarcomas; STO Solid tumor other.

2. INTRODUCTION

According to the RARECARE dataset (website: <http://www.rarecare.eu>), the most common extracranial solid tumors in children (aged 0 to 14 years) include neuroblastoma (NB), Wilms tumor, and sarcomas, including rhabdomyosarcoma, osteosarcoma, and Ewing sarcoma. Survival rates are highly variable with the type of solid tumor, although high overall survival (OS) rates are reported at 1 year (92%) and 5 years (76%) overall.

Pediatric hematopoietic and lymphoid malignancies are typically of an aggressive type, with acute lymphoblastic leukemia being the most common childhood cancer. According to RARECARE, other prevalent cancers of this type in ages 0 to 14 years include non-Hodgkin's lymphoma (NHL), Hodgkin's lymphoma (HL), and acute myeloid leukemia. Data from RARECARE also show high survival rates in children with HL (99% at 1 year) and remains high 5 years after diagnosis. For other lymphoid tumors, survival is also relatively high (>70%).

Standard therapy for solid and hematological pediatric tumors includes various combinations of surgery, cytotoxic chemotherapy, and radiation. These treatments can have detrimental consequences to a developing child, and many survivors carry a substantial burden of long-term morbidities. With improved survival rates, children with cancer are likely to live longer, with the risk of long-term toxicity being an important crucial factor. In addition, there is an overall unmet medical need for more effective therapies for pediatric patients who have relapsed/refractory disease. Attractive alternatives would include biological agents that do not include toxic chemotherapy and target alternative carcinogenesis pathways that may have acquired resistance from the previous therapies. Immune checkpoint inhibitors may be such candidates, with promising and positive outcomes in adults with melanoma, lung cancer, bladder cancer, gastric cancer, microsatellite instability in colorectal cancer, and other malignancies (SIOPE briefing, 2015).

2.1 Study rationale

Therapeutic options are lacking for the treatment of relapsed/refractory solid tumors and hematological malignancies in the pediatric population. Additionally, conventional pediatric therapies often produce long-term side effects. Therapies with less frequent and non-overlapping long-term side effect profiles would likely improve the quality of life of these patients.

Based on results of immune checkpoint inhibitor therapies in adults with relapsed/refractory solid tumors and lymphomas (see Section 2.2.1), durvalumab monotherapy or durvalumab plus tremelimumab combination therapy may represent an effective treatment for the pediatric population. The proposed study will evaluate durvalumab in combination with tremelimumab in pediatric patients with refractory/relapsed solid tumors and lymphoid malignancies.

This study has been discussed and agreed with the European Medicines Agency (EMA) Paediatric Committee (PDCO) and forms a key commitment as part of the Pediatric Investigation Plan.

2.2 Background

A detailed description of the chemistry, pharmacology, efficacy, and safety of durvalumab and tremelimumab is provided in the respective Investigator's Brochures (IBs).

2.2.1 Immunotherapies

It is increasingly understood that cancers are recognized by the immune system, and under some circumstances, the immune system may control or even eliminate tumors (Dunn et al 2004).

Programmed cell death ligand 1 (PD-L1) is part of a complex system of receptors and ligands that are involved in controlling T-cell activation. The programmed cell death 1 (PD-1) receptor (cluster of differentiation [CD]279) is expressed on the surface of activated T-cells (Keir et al 2008). It has 2 known ligands: PD-L1 (B7-H1; CD274) and programmed cell death ligand 2 (PD-L2) (B7-DC; CD273) (Okazaki and Honjo 2007). PD-1 and PD-L1/PD-L2 belong to a family of immune checkpoint proteins that act as co-inhibitory factors, which can halt or limit the development of T-cell response. When PD-L1 binds to PD-1, an inhibitory signal is transmitted into the T-cell, which reduces cytokine production and suppresses T-cell proliferation. Tumor cells exploit this immune checkpoint pathway as a mechanism to evade detection and inhibit immune response.

PD-L1 is constitutively expressed by B-cells, dendritic cells, and macrophages (Qin et al 2016). Importantly, PD-L1 is commonly over-expressed on tumor cells or on non-transformed cells in the tumor microenvironment (Pardoll 2012). PD-L1 expressed on the tumor cells binds to PD-1 receptors on the activated T-cells, leading to the inhibition of cytotoxic T-cells. These deactivated T-cells remain inhibited in the tumor microenvironment. The PD-1/PD-L1 pathway represents an adaptive immune resistance mechanism that is exerted by tumor cells in response to endogenous antitumor activity.

The inhibitory mechanism described above is co-opted by tumors that express PD-L1 as a way of evading immune detection and elimination. The binding of an anti-PD-L1 agent to the PD-L1 receptor inhibits the interaction of PD-L1 with the PD-1 and CD80 receptors expressed on immune cells (ICs). This activity overcomes PD-L1-mediated inhibition of antitumor immunity. While functional blockade of PD-L1 results in T-cell reactivation, this mechanism of action is different from direct agonism of a stimulatory receptor such as CD28.

PD-L1 is expressed in a broad range of cancers. Based on these findings, an anti-PD-L1 antibody could be used therapeutically to enhance antitumor immune responses in patients with cancer. Results of pre-clinical and clinical studies of monoclonal antibodies (mAbs) targeting the PD-L1/PD-1 pathway have shown evidence of clinical activity and a manageable safety profile, supporting the hypothesis that an anti-PD-L1 antibody could be used to therapeutically enhance antitumor immune response in cancer patients (Brahmer et al 2012, Hirano et al 2005, Iwai et al 2002, Okudaira et al 2009, Topalian et al 2012, Zhang et al 2008) with responses that tend to be more pronounced in patients with tumors that express PD-L1 (Powles et al 2014, Rizvi et al 2015, Segal et al 2015). In addition, high mutational burden (eg, in bladder carcinoma; Alexandrov et al 2013) may contribute to the responses seen with immune therapy.

In contrast, anti-cytotoxic T-lymphocyte-associated antigen 4 (CTLA-4) is constitutively expressed by regulatory T-cells and upregulated on activated T-cells. CTLA-4 delivers a negative regulatory signal to T-cells upon binding of CD80 (B7.1) or CD86 (B7.2) ligands on antigen-presenting cells (Fife and Bluestone 2008). Blockade of CTLA-4 binding to CD80/86 by anti-CTLA-4 antibodies results in markedly enhanced T-cell activation and antitumor activity in animal models, including killing of established murine solid tumors and induction of protective antitumor immunity. Therefore, it is expected that treatment with an anti-CTLA-4 antibody will lead to increased activation of the human immune system, increasing antitumor activity in patients with solid tumors.

Pre-clinical data have now been added to a wealth of clinical data showing that blockade of negative regulatory signals to T-cells such as CTLA-4 and PD-L1 has promising clinical activity. Ipilimumab was first granted United States (US) Food and Drug Administration (FDA) approval for the treatment of metastatic melanoma and is currently under investigation for several other malignancies. Nivolumab and pembrolizumab, 2 anti-PD-1 agents, and atezolizumab, an anti-PD-L1 agent, have been granted approvals by agencies for the treatment of a number of malignancies in adult patients, including metastatic melanoma, squamous and non-squamous cell non-small-cell lung cancer, squamous cell carcinoma of the head and neck, and urothelial carcinoma. In addition, there are data from agents in the anti-PD-1/PD-L1 class showing clinical activity in a wide range of tumor types.

It is anticipated, based on preliminary efficacy signals for anti-PD-1/PD-L1 antibodies in pediatric indications, that immunotherapy agents could also play an important role in the treatment of relapsed/refractory solid tumors and hematological malignancies in the pediatric population, which are currently lacking. Presently the following data are available to support use of immunotherapy agents in pediatric patients.

A Phase I/II study of pembrolizumab in pediatric patients with advanced melanoma or a PD-L1+ advanced, relapsed, or refractory solid tumor or lymphoma. As of 07 November 2016, 1 patient each with HL, adrenocortical carcinoma, mesothelioma, and glioblastoma had partial response (PR) for an objective response rate (ORR) of 6.1% (95% confidence interval [CI], 1.7-14.8); 7 (10.6%) patients had stable disease (SD) for a disease control rate (DCR) of 16.7% (95% CI, 8.6-27.9). Median progression-free survival (PFS) and OS were 1.8 months and 9.2 months, respectively; 12-month PFS was 10.2% and OS was 40.5% (Geoerger et al 2017a).

Ipilimumab, an anti CTLA-4 inhibitor is approved by the FDA for the treatment of unresectable or metastatic melanoma in adults and pediatric patients (12 years and older) and for the treatment of adult and pediatric patients 12 years of age and older with microsatellite instability-high (MSI-H) or mismatch repair deficient (dMMR) metastatic colorectal cancer that has progressed following treatment with a fluoropyrimidine, oxaliplatin, and irinotecan, in combination with nivolumab (USPI). Ipilimumab in combination with nivolumab is being pursued in a Phase I/II study of known pediatric patients with relapsed/refractory solid tumors (Davis et al 2017).

In a Phase I/II study assessing the safety, pharmacokinetic and preliminary activity of atezolizumab in pediatric and young adult patients with refractory/relapsed solid tumors concluded as of 19 July 2016 that the PK and safety profile of atezolizumab is similar to that in

adults. Two in 5 patients with HL had a PR and the only patient with atypical rhabdoid tumor had an unconfirmed PR.

There is a significant unmet medical need for new effective therapies for pediatric patients and these preliminary data suggest immunotherapy agents and combinations thereof may provide alternative effective cancer therapies for young adults and children. There is also strong rationale and support from the EMA PDCO and clinical experts to evaluate the synergistic activity of combined anti-PD-L1 and CTLA-4 targeting to activate the patient's native immune system against their cancer.

